14.3. Ethical Conduct of the Study

The study will be performed in accordance with ethical principles that have their origin in the Declaration of Helsinki and are consistent with ICH GCP, and applicable regulatory requirements.

14.4. Written Informed Consent

The Investigator(s) at each center will ensure that the subject is given full and adequate oral and written information about the nature, purpose, possible risk and benefit of the study. Subjects must also be notified that they are free to discontinue from the study at any time. The subject should be given the opportunity to ask questions and allowed time to consider the information provided. This process should be recorded in the subject's source documentation.

The subject's signed and dated informed consent must be obtained before conducting any study procedures. Documentation of the consenting process must be recorded in the subject's source documents.

The Investigator(s) must maintain the original, signed Informed Consent Form. A copy of the signed Informed Consent Form must be given to the subject, and this must be documented in the subject's source documents.

14.5. Subject Confidentiality

In order to maintain subject privacy, all eCRFs, study drug accountability records, study reports, and communications will identify the subject by initials (as allowed by local regulations) and the assigned subject number. The Investigator will grant monitor(s) and auditor(s) from the Sponsor or its designee and regulatory authority(ies) access to the subject's original medical records for verification of data gathered on the eCRFs and to audit the data collection process. The subject's confidentiality will be maintained and will not be made publicly available to the extent permitted by the applicable laws and regulations.

15. ADMINISTRATIVE REQUIREMENTS

15.1. Study Monitoring

Monitoring and auditing procedures developed by the Sponsor or designee will be followed, in order to comply with GCP guidelines.

Before a study center can enter a subject into the study, a representative of Sagimet Biosciences or designee will visit the study center to:

- Determine the adequacy of the facilities.
- Discuss with the Investigator(s) and other personnel their responsibilities with regard to protocol adherence, and the responsibilities of Sagimet Biosciences or its representatives. This will be documented in a Clinical Study Agreement between Sagimet Biosciences and the Investigator.

During the study, a monitor from Sagimet Biosciences or designee will have regular contacts with the study center, for the following:

- Provide information and support to the Investigator(s).
- Confirm that facilities remain acceptable.
- Confirm that the investigational team is adhering to the protocol, that data are being accurately recorded in the source documents and eCRFs, and that investigational product accountability checks are being performed.
- Perform source data verification. This includes a comparison of the data in the eCRFs with the subject's medical records at the hospital or practice, and other records relevant to the study. This will require direct access to all original records for each subject (e.g., clinic charts).
- Record and report any protocol deviations not previously sent to Sagimet Biosciences.
- Confirm AEs and SAEs have been properly documented in the eCRFs and confirm any SAEs have been forwarded to the Sponsor or designee, and those SAEs that met criteria for reporting have been forwarded to the IRB.

The monitor will be available between visits if the Investigator(s) or other staff needs information or advice.

15.2. Case Report Form Completion

The Sponsor or designee will provide the study centers with eCRFs for each subject.

eCRFs will be completed for each study subject. It is the Investigator's responsibility to ensure the accuracy, completeness, and timeliness of the data reported in the subject's eCRF. Source documentation supporting the eCRF data should indicate the subject's participation in the study and should document the dates and details of study procedures, AEs, and subject status.

The Investigator, or designated representative, should complete the eCRF as soon as possible after information is collected, preferably on the same day that a subject is seen for an

examination, treatment, or any other study procedure. Any outstanding entries must be completed immediately after the final examination. An explanation should be given for all missing data.

The Investigator must electronically sign and date the Investigator's Statement at the end of the eCRF to endorse the recorded data.

15.3. Computerized Systems / Medical Records as Source Data

All study data recorded on source documents are to be transcribed into the eCRFs. Any electronic study data are to be entered into a secure, validated data processing system and a backup maintained. Any changes to electronic study data will be documented.

15.4. Retention of Records

The Investigator will maintain all study records according to ICH GCP and applicable regulatory requirement(s). Records will be retained for at least 2 years after the last marketing application approval or 2 years after formal discontinuation of the clinical development of the investigational product or according to applicable regulatory requirement(s). If the Investigator withdraws from the responsibility of keeping the study records, custody must be transferred to a person willing to accept the responsibility. The Sponsor must be notified immediately by telephone or e-mail and the notification confirmed in writing if a custodial change occurs.

15.5. Audits and Inspections

Authorized representatives of Sagimet Biosciences or designee, a regulatory authority, or IRB may visit the study center to perform audits or inspections, including source data verification. The purpose of an audit or inspection is to systematically and independently examine all study-related activities and documents to determine whether these activities were conducted, and data were recorded, analyzed, and accurately reported according to the protocol, ICH GCP, and any applicable regulatory requirements.

The investigator should contact Sagimet Biosciences or designee immediately if contacted by a regulatory agency about an inspection.

[REDACTED]

[REDACTED]

[REDACTED]

17. APPENDICES

Appendix A: Algorithm for Evaluating Subjects for a Potential Drug-induced Liver Injury (DILI)

The mean of at least 2 liver aminotransferase values taken at least 4 to 12 weeks apart during screening should be used to establish baseline values; the first measurement may be a historical measurement.

During the study, aminotransferase elevations are to be managed as follows:

1. Isolated aminotransferase elevation (i.e., total bilirubin - normal):

ALT or AST	Event during the study	Action
Baseline ALT and AST within normal range	Increase $\geq 5 \times$ ULN	Repeat liver profile (AST, ALT, bilirubin and PT/INR) within 2 to 3 days. Monitor the subject as per “close observation” definition* in the DILI guidance.
ALT or AST above normal range at baseline	increase $\geq 3 \times$ baseline levels and no liver related symptoms	Interrupt study drug. Initiate potential DILI evaluation for alternative etiologies and repeat liver profile and PT/INR within 48-72 hours and closely observe the subject.
ALT or AST above normal range at baseline	increase $\geq 3x$ baseline + subject experiences liver related symptoms (nausea, vomiting, right upper quadrant pain)	

*Close observation as defined in the FDA DILI guidance i.e., laboratory testing and physical examination 2-3 times per week. Study drug is to be restarted only if a firm alternative etiology is “identified” and the liver tests return to baseline.

2. Elevation of aminotransferase and total bilirubin or cholestatic markers:

Analyte	Event during the study	Action
TB + AST or ALT	\uparrow TB >2 mg/dL and \uparrow ALT or ALT $\geq 3x$ baseline or $5x$ ULN (whichever comes first)	Interrupt study drug. Initiate potential DILI evaluation for alternative etiologies. Repeat liver profile and PT/INR within 48-72 hours and place subject under “close observation” as defined in the DILI guidance.
TB, ALP, or GGT	\uparrow TB >2 mg/dL and ALP or GGT $\uparrow >2X$ ULN	Study drug can be restarted only if a firm competing etiology is identified and the liver tests return to baseline.

Analyte	Event during the study	Action
TB OR INR + symptoms (regardless of any magnitude AST/ALT elevation)	Elevation ↑ TB >2 mg/dL OR INR ≥1.5 and Indicators of immunological reaction (i.e., rash or >5% eosinophilia), or appearance of nausea, vomiting, right upper quadrant pain (symptoms consistent with clinical hepatitis)	Permanently discontinue study drug. Initiate potential DILI evaluation for alternative etiologies. Repeat liver profile and PT/INR within 48-72 hours and place subject under “close observation” as defined in the DILI guidance.

Note the following:

1. If a subject lives in a remote area, they can be tested locally, with the results communicated to the Investigator promptly.
2. For subjects with Gilbert’s syndrome, a doubling of direct bilirubin instead of total bilirubin should be used for close monitoring and TVB-2640 discontinuation.
3. If the following criteria are met, study drug must be discontinued and the subject must be followed until the clinical and laboratory abnormalities stabilize or normalize:
 - If close monitoring of a subject is not possible.
 - In the presence of total bilirubin elevation (>2 × ULN or >1.5 × baseline); with any degree of aminotransferase elevation; AND if there is appearance of symptoms i.e., fatigue, nausea, vomiting, right upper quadrant pain or tenderness, fever, rash, and/or eosinophilia (>5%).
 - If any degree of total bilirubin, ALT, or AST elevation recurs following re-challenge with study drug.

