8.6. Subject Withdrawal Criteria

Subjects will be informed that they have the right to withdraw from the study at any time for any reason, without prejudice to their medical care. Study drug must be permanently discontinued

and the subject withdrawn from the study for any of the following TEAEs, with the subject managed as indicated:

- **Palmar-plantar Erythrodysesthesia (PPE):** For mild to moderate symptoms of PPE (e.g., redness, pain, or scaling of hands or feet), study drug should be interrupted and symptomatic measures, including hand cream such as “Udder Cream”, instituted immediately. Study drug may be resumed after resolution of symptoms. Study drug should be permanently discontinued at the first sign of significant/severe, redness, pain, or scaling of hands or feet, and symptomatic measures instituted immediately.
- **Dyspnea or suspected pneumonitis:** Study drug should be permanently discontinued for subjects with shortness of breath or other respiratory symptoms that are otherwise unexplained. The subject is to be carefully monitored for improvement. In the event that symptoms worsen or present as more than mild intensity, immediate referral to a qualified pulmonologist for definitive diagnosis and treatment should be undertaken.
- **Visual symptoms (including keratitis):** Study drug should be permanently discontinued at the first sign of significant, redness, pain, or dryness of the eyes. Symptomatic measures, including moisturizing eye drops should be instituted. In the event that symptoms worsen or present as more than mild, immediate referral to a qualified ophthalmologist should be undertaken.
- **Evidence of drug-induced liver injury (DILI);** Study drug should be permanently discontinued for subjects with evidence of DILI; see [Appendix A](#) for details.

Refer to the Study Manual for additional details regarding the assessment and management of these events.

Furthermore, the Investigator also has the right to withdraw subjects from the study for any of the following reasons:

- Progression of underlying disease that, in the opinion of the Investigator, precludes further study treatment.
- Occurrence of any other unacceptable AE.
- Study drug interruption for any reason for >7 days.
- Subject requires use of a prohibited concomitant medication or therapy.
- General or specific changes in the subject’s condition unacceptable for further treatment within the study parameters, in the judgment of the Investigator.
- Non-compliance.

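### Appendix A does not require drug interruption for a normal-baseline subject with ALT or AST at least 5 × ULN and liver symptoms when bilirubin is normal and INR is below 1.5

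*Protocol*

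**What the plan says.** Appendix A, part 1 applies when total bilirubin is normal, and it splits subjects by baseline aminotransferases.

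- **Normal baseline ALT and AST, rise to 5 × ULN or more:** "Repeat liver profile (AST, ALT, bilirubin and PT/INR) within 2 to 3 days", with close observation, which the table's footnote defines as tests and examination 2-3 times per week.
- **Raised baseline, rise to 3 × baseline or more:** there is one row without symptoms and one with them, the latter worded "baseline + subject experiences liver related symptoms (nausea, vomiting, right upper quadrant pain". The action shown against these rows is "Interrupt study drug. Initiate potential DILI evaluation for alternative etiologies and repeat liver profile and PT/INR within 48-72 hours and closely observe the subject".

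Part 2 covers combined abnormalities. Its symptom row is labelled "TB OR INR + symptoms (regardless of any magnitude AST/ALT elevation" and requires total bilirubin above 2 mg/dL or INR of at least 1.5. Note 3 lists mandatory stops. One needs raised bilirubin with symptoms. The others are "If close monitoring of a subject is not possible" and "If any degree of total bilirubin, ALT, or AST elevation recurs following re-challenge with study drug".

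Section 8.6 adds: "Study drug should be permanently discontinued for subjects with evidence of DILI", and sends the reader to Appendix A for details. Its remaining routes are discretionary: "Furthermore, the Investigator also has the right to withdraw subjects from the study for any of the following reasons".

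**The concern.** In part 1, symptoms are a named criterion only for subjects who start with raised enzymes. For a subject who starts normal, nausea, vomiting or right upper quadrant pain at 5 × ULN changes nothing in the prescribed action. The row also has no upper limit.

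This sits oddly with the rest of the protocol. In part 2, once bilirubin exceeds 2 mg/dL, 3 × baseline and 5 × ULN are alternative triggers for interruption, whichever is reached first. Part 1 does not pair them, and no reason is given. Section 8.6 interrupts drug even for mild to moderate palmar-plantar symptoms and stops it for unexplained respiratory symptoms.

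What is at stake is individual subject safety. A site following the table literally could continue dosing a symptomatic subject with a large rise. Safety, including effects on ALT and AST, is a primary objective (Protocol Section 6.1).

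**Working it through.** The plan states no figure to reproduce, so the check is a walk through the rules followed by simple arithmetic on the triggers.

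**Test case.** Normal baseline ALT and AST; ALT or AST at 5 × ULN or more; liver symptoms; normal bilirubin; INR below 1.5; first event.

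| Rule | Requirement | Mandatory stop here? |
|---|---|---|
| App. A part 1, row 1 | Normal baseline, ≥5 × ULN | Applies, but only repeat tests and observation |
| App. A part 1, rows 2 and 3 | Raised baseline | No |
| App. A part 2, bilirubin with ALT/AST | Bilirubin >2 mg/dL | No |
| App. A part 2, bilirubin with ALP or GGT | Bilirubin >2 mg/dL | No |
| App. A part 2, symptom row | Bilirubin >2 mg/dL or INR ≥1.5 | No |
| App. A note 3, bilirubin with symptoms | Bilirubin >2 × ULN or >1.5 × baseline | No |
| App. A note 3, monitoring | Close monitoring not possible | Only if that is so |
| App. A note 3, re-challenge | Recurrence after re-challenge | No, at a first event |
| Section 8.6, DILI rule | Evidence of DILI, no threshold; refers to Appendix A | No defined trigger |
| Section 8.6, other routes | Investigator's right to withdraw | Discretionary |
| Section 7.2 | One Grade 5, two of the same Grade 4, or three of the same Grade 3 events | Suspends a dose level; not an individual rule |

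The action cell of the third row in part 1 is blank in the extracted text, probably because cells were merged. If the interrupting action covers both raised-baseline rows, or only the symptomatic one, row 1 still keeps its own repeat-and-observe action. The result is the same.

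**Size of the mismatch.** Let b be the baseline in multiples of ULN, and read the trigger as the level reached.

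- Normal baseline (b ≤ 1): the trigger is 5, so the fold rise is 5/b. At b = 1 it is 5.0; at 0.9, 5/0.9 = 5.6; at 0.5, 5/0.5 = 10.0.
- Raised baseline with symptoms (b > 1): the trigger is 3b, so the fold rise is 3.0. The level is 3 × 1.1 = 3.3 × ULN, 3 × 1.25 = 3.75 × ULN, or 3 × 1.5 = 4.5 × ULN.
- The raised-baseline hold comes below 5 × ULN when 3b < 5, that is b < 5/3 = 1.67.

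If a rise instead means an increment added to baseline, the normal-baseline fold is (5 + b)/b, at least 6.0, and the raised-baseline fold is (b + 3b)/b = 4.0. The order is the same.

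**Such subjects can be enrolled.** In Protocol Section 8.2, criterion 6, raised ALT is only one of several entry alternatives. SAP Section 8.3.2 restricts the ALT normalization analysis to subjects above ULN at baseline, so the plan expects others who are not.

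**The case against.** The strongest counter-argument is Section 8.6. Its list opens with a mandatory instruction to discontinue and withdraw, and DILI is on that list. A treated subject who goes from normal to 5 × ULN with hepatitis-like symptoms and no other cause could reasonably be judged to show evidence of DILI. This stands as a route to stopping. But the finding that activates it is undefined and is referred to Appendix A, which orders only observation here.

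Second, the asterisk on close observation in row 1 leads to a sentence about when drug may be restarted, which presupposes a hold. That is a real ambiguity and a careful investigator might infer a hold from it. It does not order one.

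Third, fold rise is only one yardstick. Exclusions 12 and 13 in Section 8.3 allow baseline values up to 5 × ULN, so a symptomatic subject starting at 3 × ULN is held only at 9 × ULN, and one starting at 5 × ULN only at 15 × ULN. Above a baseline of 1.67 × ULN the order in absolute level reverses. This is correct and limits the absolute-level comparison to baselines below 1.67. It does not affect the absence of a rule for the normal-baseline subject.

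Fourth, the exposure window should be short. Bilirubin and INR are repeated in 2 to 3 days, tests continue 2-3 times weekly, sites know the assignment in Cohorts 1 and 2 (Section 9.9), and the SRC reviews liver events (Section 8.7). These safeguards are genuine, but none mandates a hold in this case.

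Finally, the Study Manual cited in Section 8.6 and the FDA guidance cited in Appendix A are not among the documents, and either may say more.

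**Conclusion.** The concern holds for the protocol text. No explicit mandatory interruption covers a normal-baseline subject at 5 × ULN or more with liver symptoms when bilirubin is normal, INR is below 1.5 and close monitoring is feasible. At the trigger such a subject has risen at least 5.0-fold, against 3.0-fold for the symptomatic raised-baseline subject who is interrupted. Section 8.6 and the restart sentence allow a stop by judgment or inference; neither supplies a defined trigger.

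The conclusion does not depend on how the blank table cell is merged or on how the rise is read. It is limited to the protocol's wording. The documents give neither the share of normal-baseline subjects nor the rate of such events, so no count is estimated. Sample size, power and error rates are unaffected. It should be corrected because it concerns an individual stopping rule and the correction is cheap.

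**What to change.** Add a row to Appendix A, part 1, or extend the symptomatic row, so that a subject with normal baseline ALT and AST who reaches 5 × ULN or more with liver symptoms has study drug interrupted and a DILI evaluation started. As a minor clarification, attach the restart condition to the interrupting action, as part 2 already does.

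The cost is wording in one table at the next amendment and a notice to sites. A few more subjects may be interrupted, and under Section 8.6 an interruption longer than 7 days may lead to withdrawal at the investigator's discretion. No scheduled visits, scheduled tests or subjects are added.

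The Table 2 footnotes describe the 25 mg cohort as complete and the 50 mg cohort as fully enrolled, and the March 2022 SAP addendum refers to data collected for thirteen Cohort 3 subjects. If dosing has ended, make the change in any later protocol that reuses this algorithm.

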Appendix 2. Planned Tables, Listings, and Figures	31

ABBREVIATIONS

Abbreviation	Explanation
15-HETE	15-LOX-derived 15-hydroxyeicosatetraenoic acid
Adipo-IR	Adipose tissue insulin resistance
AE	Adverse event
ALT	Alanine aminotransferase
ANCOVA	Analysis of covariance
ApoB	Apolipoprotein B
AST	Aspartate aminotransferase
ATC	Anatomic therapeutic class
ATP	As-Treated Population
BMI	Body mass index
CI	Confidence interval
CK-18	Cytokeratin-18
cm	Centimeter
CMH	Cochran-Mantel-Haenszel
CSR	Clinical Study Report
CTCAE	Common Terminology Criteria for Adverse Events
DM	Diabetes mellitus
DNL	De novo lipogenesis
ECG	Electrocardiogram
eCRF	Electronic case report form
ELF	Enhanced liver function
FASN	Fatty acid synthase
FDA	Food and Drug Association
FIB-4	Fibrosis-4
GGT	Gamma-glutamyl transpeptidase
HbA1c	Glycated hemoglobin
HDL-C	High-density lipoprotein cholesterol
HOMA-IR	Homeostatic model assessment insulin resistance
ICH	International Council for Harmonisation
IL-6	Interleukin 6
INR	International normalized ratio
ITT	Intent-to-treat population
IWRS	Interactive Web Response System
kg	Kilogram
LDL-C	Low-density lipoprotein cholesterol
LLN	Lower limit of normal
LOCF	Last Observation Carried Forward
Lp(a)	Lipoprotein(a)
LTB4	5-LOX-derived leukotriene B4
LXA4	Lipoxin A4
m	Meter
max	Maximum
MedDRA	Medical Dictionary for Regulatory Activities

Abbreviation	Explanation
min	Minimum
mITT	Modified intent-to-treat population
mmHg	Millimeters of mercury
MMRM	Mixed model for repeated measures
MRE	Magnetic resonance elastography
ms	Millisecond
N or n	Number of subjects
NASH	Non-alcoholic steatohepatitis
NCI	National Cancer Institute
NEFA	Non-esterified fatty acid
MRI-PDFF	Proton density fat fraction by magnetic resonance imaging
PGE2	prostaglandin E2
PK	Pharmacokinetic
PO	Orally
PP	Per-protocol
PT	Preferred term
Q1	First quartile
Q3	Third quartile
QD	Once daily
SAE	Serious adverse event
SAP	Statistical analysis plan
SD	Standard deviation
SE	Standard error
SI	International System of Units
SOC	System organ class
SRC	Safety Review Committee
TEAE	Treatment-emergent adverse event
TLF	Tables, listings, and figures
TG	Triglycerides
TNF α	Tumor necrosis factor-alpha
ULN	Upper limit of normal
VCTE	Vibration-controlled transient elastography
β -HCG	Beta-human chorionic gonadotropin

Sponsor: Sagimet Biosciences
Protocol Number: 3V2640-CLIN-005
Version and Date: Final Version 1, 02June2020

1. INTRODUCTION

The statistical analysis plan (SAP) details the planned analysis required to satisfy the Clinical Study Report (CSR) of Sagimet Biosciences, Inc. (Sagimet) study number 3V2640-CLIN-005: A Phase 2, Multi-Center, Single-Blind, Randomized, Placebo-Controlled Study of TVB-2640 in Subjects With Non-Alcoholic Steatohepatitis (NASH). The content of this SAP is based on the protocol version 6.0 dated 29Apr2020.

SAP Revision Chronology:

Final Version 1

02June2020

Original

